### 3 STUDY ENDPOINTS

#### 3.1 Primary Endpoints

- The primary endpoint is PFS, based on central radiological assessment per mRECIST, version 1.1, in patients with advanced GIST. Progression-free survival is defined as time from randomization to disease progression, or death due to any cause, whichever occurs first.

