At least 70% of the patients enrolled should be receiving the study drug as their third distinct TKI treatment for GIST, ie, no more than 30% of patients should be receiving the study drug as their fourth distinct TKI treatment for GIST. In addition, patients will

receive BSC, excluding any additional anticancer therapy such as any systemic antineoplastic therapy (including kinase inhibitors and chemotherapy), radiation therapy, or surgery.

All patients will present to the study center on C1D1 for the first dose of study drug, vital sign measurements, physical exam, quality-of-life (QoL) assessment, PRO assessments, laboratory assessments, ECG and AE recording. In Cycle 2 Day 1 (C2D1), Cycle 3 Day 1 (C3D1), Cycle 4 Day 1 (C4D1) and Cycle 5 Day 1 (C5D1), patients will present to study centers for physical examination, vital signs measurements, laboratory assessments, QoL assessments, PRO assessments, ECG, and AE/concomitant medication recording. On C1D15 and C2D15, all patients will attend study center visits for vital sign measurements, serum chemistry measurements, and AE reporting. For all subsequent cycles, all patients will attend study center visits every other cycle on Day 1 of odd cycles (ie, C7D1, C9D1 etc.) for physical examination, vital sign measurements, laboratory assessments, QoL assessments, PRO assessments, ECG and AE recording. At any point in time between treatment cycles patients should attend or contact the study center for AE reporting, evaluation, and medical intervention.

[figure not shown]
Tumor assessments will be performed at Baseline and then every 8 weeks ( $\pm$  1 week) counting from C1D1, regardless of the scheduled treatment cycles, ie, if study treatment is interrupted or discontinued for any reason, tumor imaging should continue according to an 8-week schedule until tumor progression is confirmed by central radiology review. Computed tomography with intravenous (IV) contrast is the preferred imaging modality, unless a site of disease is better evaluated by MRI.

It is anticipated that patients will receive at least 1 cycle of avapritinib if randomized to Arm A and regorafenib if randomized to Arm B; no maximum treatment duration has been set. After C1, patients may continue to receive study drug until precluded by toxicity, noncompliance, pregnancy, withdrawal of consent, physician decision, PD, death, or closure of the study by the Sponsor.

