## 6 STUDY CONDUCT

### 6.1 General Conduct

The study will be conducted at multiple centers in North America, Europe, Australia, and Asia.

This study will be conducted in compliance with the protocol, Good Clinical Practice (GCP), and the applicable regulatory requirements.

Patients may be randomized in the system at any time but must be dosed within 28 days of signing of informed consent.

The schedule of assessments for the study is provided in [Table 2](#).

The minimum duration of patient participation is expected to be approximately 3 months, including a screening period to assess study eligibility up to 4 weeks (28 days); a treatment period of at least 1 cycle (28 days); an EOT visit at least  $14 \pm 7$  days after the last dose of study drug; and a Safety Follow-up visit in the clinic for physical examination and resolution of any AEs 30 days ( $\pm 7$  days) after the last dose of study drug. Thereafter, patients are to be followed for tumor imaging every 8 weeks ( $\pm 7$  days) until disease progression, death, initiation of new anti-GIST therapy, withdrawal of consent, or closure of the study by the Sponsor and then survival approximately every 2 months until death, withdrawal of consent or closure of the study by the Sponsor.

The end of the study is defined as the time that the last patient completes his/her last visit (LPLV), including assessments performed as part of PFS follow-up, if the patient enters the PFS follow-up part of the study. See [Section 7](#) for details of all study assessments.

The expected enrollment period is approximately 18 months and the expected duration of the study to reach the primary analysis timepoint is approximately 24 months until a total number of 264 PFS events are reached. The study will be completed when all patients are no longer receiving study drug and follow-up for OS has been concluded.

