### **8.1.2 Regorafenib**

Regorafenib will be provided to the study center as 40 mg strength tablets, packaged in bottles, and will be labeled according to local regulations. In the US, locally obtained commercial supplies of regorafenib may be used and reimbursed by the Sponsor. Regorafenib is to be stored in the original bottle at 25°C (77°F); excursions are permitted from 15°C to 30°C (59°F to 86°F). See [Appendix 1](#) for additional details.

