### **10.2 Sample Size Estimation**

A total of approximately 460 patients will be needed for the study. Patients will be recruited from approximately 90 sites and it is expected that each site will enroll about 3-10 patients.

The sample size calculation was based upon the assumption that the median PFS for regorafenib is approximately 5 months ([Stivarga, 2017](#)). Assuming avapritinib can reduce

the risk of PFS by 33%, ie, assuming the HR of 0.67 (avapritinib compared to regorafenib), a minimum of 264 PFS events are needed to provide 90% power at a 2-sided alpha of 0.05 for the study. With an 18-month accrual period and a 6-month follow-up period, the total sample size needed for the study is approximately 460 patients (230 patients per arm) in order to achieve 264 total PFS events. The sample size calculation has taken a 2% dropout rate into consideration and assumes accrual will follow a truncated exponential distribution with a scaled power parameter -9.

The sample size calculated for the primary endpoint, PFS, is also sufficient for detecting a difference in ORR between the two arms. Assuming a null ORR of 5% and an alternative ORR of 15%, approximately 95% power is obtained using a test of two-proportions.

We assume the same effect size for OS as for PFS, hence the same number of events (264) is required to power the analysis. The timing of the OS analysis, however shall be later than the PFS analysis as it will be at such time that 264 deaths occur.

Gate keeping sequential testing will be implemented to test PFS, then ORR, and then OS.

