**Table 2: Progression Free Survival Censoring Rules**

Situation	Date of Progression or Censoring	FDA Censoring Rules	EMA Censoring Rules
No baseline assessments and alive after 2 scheduled assessments (defined by 130 days)	Date of randomization	Censored	Censored
Progression documented between scheduled visits	Date of radiological assessment showing new lesions or an increase in measured lesions	Event	Event
No progression	Date of last radiological assessment with evidence of no progression (or randomization date if no assessment)	Censored	Censored
New anticancer/ non-protocol treatment started prior to progression	Date of last radiological assessment with evidence of no progression prior to the start of new anticancer treatment	Censored	Event at date of disease progression/death
Death before the second scheduled post-baseline assessment (defined by within 130 days of date of randomization)	Date of death	Event	Event
Death between scheduled assessments	Date of death	Event	Event
Death or progression immediately after an extended lost to follow-up time (2 more missed scheduled assessments defined by at least x  days)	Date of last radiological assessment with evidence of no progression (randomization date if first 2 scheduled assessments are missing)	Censored	Event at date of disease progression/death

 x = 130 days if the death or progression date is ≤336 days from first dose date; x = 210 days if the death or progression date is ≥337 days from randomization date.

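### PFS is timed from randomization but scans are scheduled from C1D1, with no direct cap on the gap, so any arm difference in time to first dose would shift progression dates in the primary comparison

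*Protocol*

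**What the plan says.** **Endpoint origin.** Protocol Section 3.1: "Progression-free survival is defined as time from randomization to disease progression, or death due to any cause, whichever occurs first". Protocol Section 10.5.3.1 and SAP Sections 1.4.1 and 4.6.2 use the same origin.

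**Scan origin.** Protocol Section 4.1 sets scans every 8 weeks (±1 week), "counting from C1D1, regardless of the scheduled treatment cycles, ie, if study treatment is interrupted or discontinued for any reason". The Study Summary, Table 2 note t and Section 7.5.1 also count from C1D1.

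**The interval between the two.** Protocol Section 6.1, repeated in Section 7.1: "Patients may be randomized in the system at any time but must be dosed within 28 days of signing of informed consent". Nothing limits the time from randomization to first dose directly. Section 5.4 requires the Medical Monitor or designee to confirm eligibility before randomization.

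**Never-dosed patients.** Section 10.3 puts every randomized patient in the ITT set. Section 4.1 continues imaging when treatment is interrupted or stopped, and Section 7.8 starts PFS follow-up after a safety visit timed from the last dose. Neither gives scan dates for a patient who never starts.

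**SAP Table 2.** The early-death row reads "Death before the second scheduled post-baseline assessment (defined by within 130 days of date of randomization". The row for missing baseline assessments also uses 130 days but names no starting point. The footnote that sets the extended-loss threshold measures one limit (336 days) from first dose and the other (337 days) from randomization.

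**The concern.** Progression is dated at the scan that shows it. A patient whose C1D1 comes later after randomization has the whole scan grid moved later on the PFS axis. If this happens equally in both arms, the comparison is unaffected. If one arm starts dosing later on average, its progressions are recorded later even when the disease behaves identically.

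The gap arises once patient and physician know the arm, and the arms are not supplied identically. Protocol Section 8.1.2 says of regorafenib: "In the US, locally obtained commercial supplies of regorafenib may be used and reimbursed by the Sponsor". Blinded central reading does not correct the timing of a scan, and no sensitivity analysis in SAP Section 4.6.2 addresses it. At stake are the size and error rate of the primary test, which also gates ORR and OS.

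**Working it through.** **1. The plan's own figure.** Protocol Section 10.2 states that "a minimum of 264 PFS events are needed to provide 90% power at a 2-sided alpha of 0.05 for the study", "assuming the HR of 0.67 (avapritinib compared to regorafenib", and that "the median PFS for regorafenib is approximately 5 months".

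- Schoenfeld: 4 × (1.960 + 1.282)² / (ln 0.67)² = 42.03 / 0.1604 = 262.1, rounded up to 263 events. Power with 264 events is 90.2%.
- Expected events at 24 months with N = 460, reading the accrual parameter as -9 over 18 months: 270.5, and 270.5 × 0.98 = 265.1 after 2% dropout.

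Both stated figures reproduce.

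**2. Effect of the scan origin.** Simulation inputs:

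- From the documents: 5-month control median, 18-month accrual, 56-day scan interval with a ±7 day window, 230 per arm, analysis at 264 events.
- Assumed: exponential progression at one constant hazard from randomization; uniform accrual; mean gap of 4 days (±3) in one arm and longer in the other; scans spread evenly over the window; no deaths before progression; unstratified test.
- The arm difference is not in the documents, so a range is shown.

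Hazard ratios are avapritinib versus regorafenib.

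| Arm difference (days) | HR if true HR is 1.00: avapritinib later / regorafenib later | Two-sided type I error | HR if true HR is 0.67: avapritinib later / regorafenib later | Power at true HR 0.67, regorafenib later |
|---|---|---|---|---|
| 0 | 1.00 | 5.1% | 0.68 | 88% |
| 3 | 0.96 / 1.05 | about 7% | 0.64 / 0.70 | 79% |
| 5 | 0.94 / 1.07 | about 11% | 0.64 / 0.71 | 73% |
| 7 | 0.92 / 1.08 | 14-15% | 0.63 / 0.72 | 67% |

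A 1-day difference moves the HR by about 1%.

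**3. Sensitivity to the assumptions.**

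- *Scans closer to schedule.* With a 3-day arm difference, a ±3 day spread gives a null HR of 0.91 / 1.11 and type I error of about 18%. With every scan exactly on its day, 0.86 / 1.17 and about 37%.
- *Deaths dated exactly.* If deaths are assumed to be 10% or 20% of the hazard, a 7-day avapritinib delay gives a null HR of 0.94 or 0.95.
- *Higher hazard before dosing.* Protocol Section 1.1.2 cites a placebo median PFS of 0.9 months; 0.9 × 30.44 = 27.4 days. Applying that median during the gap, avapritinib delays of 3, 5 and 7 days give null HRs of about 1.01-1.02, 1.02-1.03 and 1.04. Assumed pre-dose medians of 60 and 100 days give about 0.98-0.96 and 0.96-0.93.
- *Scans counted from randomization* (same hazard before and after dosing). The null HR stays at 1.00 and the one-sided error at 2.3-2.6% for the same delays.

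**4. SAP Table 2.**

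- The second scan window closes 2 × 56 + 7 = 119 days after C1D1, that is, gap + 119 days after randomization. Since 130 - 119 = 11, a gap above 11 days puts the end of the window past day 130.
- For a gap of g days, 336 days from first dose is day 336 + g from randomization. Dates from day 337 to day 336 + g therefore satisfy both halves of the footnote, which assign different thresholds (130 and 210 days).

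**The case against.** The strongest reply is that nothing in the documents shows the arms will differ in time to first dose, and with equal gaps the bias is nil. That stands.

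It also stands that 28 days is only an outer bound. It runs from consent to dose, and imaging, mutation status (a stratification factor) and eligibility confirmation come before randomization. A reader might infer a typical gap of nearly four weeks; Protocol Sections 5.4 and 5.5 do not support that.

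A reader might also infer that the design favors avapritinib. The one mechanism in the documents, optional local US supply of regorafenib, would if anything delay regorafenib and work against avapritinib.

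Nor would the later arm's detections always rank just behind the other's. The ±7 day window is 14 days wide, so a shift of 3 to 7 days leaves the two sets of scan dates overlapping.

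The pre-dose hazard is a fair challenge to the size. Patients enter with progressing disease, so delay may bring real early progressions that offset or reverse the shift. But that is a true consequence of late dosing, whereas the grid shift is an artefact of measurement. That one may offset the other is no reason to keep the artefact.

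For never-dosed patients the analysis is defined. They have a screening scan, Table 2 censors them at randomization if there is no later assessment, and a death within 130 days counts as an event. Only their follow-up scan schedule is missing.

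The 130-day point is marginal. For a progression to be wrongly censored, the first scan must be missed, the second must be late and the gap must exceed 11 days.

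**Conclusion.** The mismatch of origins is real and affects the primary endpoint, but the bias is conditional. With an arm difference of 3 to 7 days (an assumption), no true effect, a constant hazard and scans spread over the full window, the HR moves to about 0.96-0.92 in favor of the later-starting arm, and two-sided type I error is about 7-15%. If regorafenib starts later, power at a true HR of 0.67 falls from 88% to 79-67%. Tighter scan timing enlarges the shift; deaths before progression reduce it; a higher pre-dose hazard can reduce or reverse the net effect. The documents do not support saying that the primary hazard ratio is biased, or in which direction. They do support saying that it is open to a bias that one scheduling choice would remove. The missing follow-up schedule for never-dosed patients and the mixed origins in SAP Table 2 are smaller defects with the same cause.

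**What to change.** - **Protocol Study Summary, Section 4.1, Table 2 note t and Section 7.5.1:** count the 8-weekly scans from randomization for all randomized patients, including those never dosed. If some patients are already on a C1D1 grid, apply the change to new patients in both arms alike.
- **Protocol Sections 6.1 and 7.1:** state that randomization follows confirmed eligibility, as Section 5.4 already requires, and takes place as close to C1D1 as practicable.
- **SAP Table 2:** use randomization as the single origin in every row and in both halves of the footnote.
- **SAP:** tabulate the interval from randomization to C1D1 by arm.

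The 16-week disease control definition has the same split (start of treatment in Protocol Section 10.5.3.2.4, randomization in SAP Section 4.6.3.4) and can be settled at the same time.

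The cost is a wording amendment and an imaging-manual update. No scans are added, and the 264 events and N = 460 are unchanged. The second scan window would close at day 119, inside the 130-day limit. The one drawback is that scan dates will no longer line up exactly with cycle Day 1 visits, although Section 4.1 already separates imaging from treatment cycles.

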## Study Schematic

Abbreviations: GIST = gastrointestinal stromal tumor; N = number of patients; R = randomized; TKI = tyrosine kinase inhibitor.

### 4.2 Justification of the Study Design

The study is designed as a randomized, open-label, efficacy and safety study. Patients who meet all study eligibility criteria will be randomly assigned in a 1:1 ratio to receive avapritinib or regorafenib. Random assignment of patients minimizes bias and helps ensure that both known and unknown risk factors are distributed evenly between treatment groups. Eligible patients will continue to receive BSC throughout the duration of the study.

The study is not blinded because the distinct AE profiles of regorafenib and avapritinib make effective blinding impossible. In particular, regorafenib treatment is associated with palmar-planar erythrodysesthesia (PPE) in 67% of patients, rash in 30% of patients and hypertension in 59% of patients (Stivarga, 2017). In addition, the adverse events requiring dose modification are very different between regorafenib and avapritinib; therefore, appropriate patient care requires that the treating physician and patient know which drug is being used. In order to prevent bias in assessing efficacy endpoints, PFS and response will be determined by independent, central radiology reviewers blinded to treatment group, and the sponsor team responsible for analysis of the study will not have access to efficacy and safety data identified by treatment group.

Demonstration of the efficacy of avapritinib as assessed by PFS is the primary objective of the study. Response assessments used to determine PFS for the primary endpoint will be based on standard response criteria (mRECIST, version 1.1) evaluated by blinded central radiology review to ensure consistent tumor assessments between the 2 randomized treatment arms.

Key secondary endpoints including ORR and OS and additional secondary endpoints including safety, DCR, DOR, disease response by Choi criteria, EORTC-QLQ-C30 scores, plasma drug concentration and an abdominal pain assessment will provide

important supportive data to help determine whether avapritinib provides a clinically relevant improvement in outcome compared to regorafenib.

An Independent Data Monitoring Committee (IDMC) will be in place to review study progress including final primary efficacy outcomes, safety data, adherence to protocol, and follow-up assessments.

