## 4 STUDY PLAN

### 4.1 Study Design

This is an open-label, randomized, Phase 3 study in patients with locally advanced unresectable or metastatic GIST (advanced GIST) of avapritinib versus regorafenib in patients previously treated with imatinib and 1 or 2 other TKIs.

All study visits are intended to be conducted on an outpatient basis. After provision of written informed consent, patients will be evaluated for study eligibility during the screening period within 4 weeks (28 days) before study drug administration on Cycle 1 Day 1 (C1D1). During the screening period, eligibility will be confirmed; management of baseline concomitant conditions will be recorded and stabilized; and baseline symptoms will be assessed. Hematology, blood chemistry, mutation status, brain imaging (CT scan or MRI), and baseline tumor assessments (CT scan or MRI) will be performed within 28 days of C1D1.

Patients are to be randomly assigned, in a 1:1 ratio, to 1 of 2 treatment arms: Arm A (avapritinib) or Arm B (regorafenib) stratified by TKI treatment (third vs. fourth), geographic region (Asia vs. rest of the world), and PDGFR $\alpha$  D842V mutation status measured in ctDNA or a tumor sample (PDGFR $\alpha$  D842V mutation present vs. absent). Patients randomized to Arm A will receive avapritinib 300 mg PO QD. Patients who experience disease progression on avapritinib, based on central review, will be offered the opportunity to continue taking treatment with avapritinib if there is no symptomatic evidence of disease progression or laboratory abnormalities attributable to disease progression, no rapid progression of disease or a progressive tumor requiring urgent alternative medical intervention at critical anatomical sites, and no decline in ECOG PS. Patients randomized to Arm A must consent to continue avapritinib treatment after disease progression; see [Section 7.7](#) for additional details.

Patients randomized to Arm B will receive regorafenib 160 mg PO QD for 3 weeks out of every 4-weeks (28 days) cycle (ie, 3 weeks on/1 week off). Patients who experience disease progression on regorafenib, as confirmed by central radiology review, may be offered the opportunity to cross over to the avapritinib treatment arm (Arm A); see [Section 7.6](#) for additional details. Prespecified dose modification guidance for AEs related to regorafenib and to avapritinib are described in [Section 6.3.1](#).

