### **7.5.2 Central Radiology Review**

A blinded central radiology review will be performed according to a prospectively established central imaging charter and conducted by an external imaging contract research organization. The central radiology review will be chartered to evaluate response assessment independently per mRECIST, version 1.1. ([Appendix 6](#)) and per Choi criteria ([Appendix 7](#)).

A detailed study-specific Imaging Core Manual will be made available to sites regarding scan acquisition requirements. All radiological scans acquired at all scheduled time points and any additional (unscheduled) radiological scans must be sent to the external imaging contract research organization.

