### 10.5.3 Efficacy Analysis

#### 10.5.3.1 Analysis of the Primary Efficacy Endpoint

The primary endpoint of PFS is defined as the time from randomization to disease progression or death due to any cause, whichever occurs first. The primary analysis for PFS is based on the central radiological assessment of PD per mRECIST, version 1.1 in the ITT population.

Patients without disease progression or death at the time of analysis will be censored at their last date of tumor evaluation. Patients who withdraw from the study and receive subsequent antineoplastic therapy without documented PD will be censored at the time of the last adequate (CT or MRI scan available) disease assessment. For PD documented between scheduled evaluations, the actual date of PD will be used, not the date of the next scheduled evaluation. For death or PD after no more than 1 missed evaluation, the date of the event will be the date of PD or death, whichever occurs first. For death or PD after more than 1 missed evaluation, the date of the event will be censored at the last adequate disease assessment. Detailed censoring methods will be described in the statistical analysis plan (SAP).

The Kaplan-Meier method will be used to estimate the distribution of PFS for each treatment group. The primary treatment comparison is based on a stratified log-rank test in the ITT population. The HR, and its 95% CI, are to be estimated based on a stratified Cox's model with treatment as the explanatory variable. Stratification factors include TKI

treatment (third vs. fourth), geographic region (Asia vs. rest of the world), and mutation status measured in ctDNA or a tumor sample (PDGFR $\alpha$  D842V mutation present vs. absent).

Progression-free survival derived from the Investigator assessment per mRECIST, version 1.1 in the ITT population, and from central radiological assessment per Choi criteria in the ITT population will be evaluated and used as supportive evidence. The analysis of PFS based on the PP population will also be included as a sensitivity analysis.

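### If more regorafenib than avapritinib progressions are found on unscheduled scans, the PFS hazard ratio is biased toward avapritinib, and no PFS analysis in the visible text would show it

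*Protocol*

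**What the plan says.** - **Safeguard.** Protocol 4.2 explains why the trial is open-label: patient and physician know the drug. Its protection for the primary endpoint is that response is "evaluated by blinded central radiology review to ensure consistent tumor assessments between the 2 randomized treatment arms".
- **Schedule.** Imaging is every 8 weeks (±1 week) from C1D1 in both arms, whatever happens to dosing (Protocol 4.1, 7.5.1, Table 2 footnote t).
- **Unscheduled scans.** They are not restricted, and "any additional (unscheduled) radiological scans must be sent to the external imaging contract research organization" (Protocol 7.5.2).
- **What confirmed progression opens.** Protocol 4.1: "Patients who experience disease progression on regorafenib, as confirmed by central radiology review, may be offered the opportunity to cross over" to avapritinib. Section 7.5.1 makes central confirmation a condition of crossover. It also says that patients in either arm with locally assessed progression stay on treatment until progression is centrally confirmed. Under 7.7, an avapritinib patient may continue the same drug.
- **Dating.** Protocol 10.5.3.1: "For PD documented between scheduled evaluations, the actual date of PD will be used, not the date of the next scheduled evaluation". In SAP Table 2 the row "Progression documented between scheduled visits" is an event at the scan date under both the FDA and the EMA rules.
- **Role of PFS.** PFS is the primary test and the gate for ORR and OS (SAP 4.6.1).

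**The concern.** Section 4.2 treats blinded reading as enough to make assessments consistent between arms. Reading is only half of the assessment; the other half is when the scan is ordered, and that decision lies with an unblinded site. On regorafenib, confirmed progression opens the study's only path to the investigational drug. On avapritinib it opens no new study drug. If that leads sites to order more scans between visits in the regorafenib arm, the same true progression gets an earlier date there than it would get on avapritinib.

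The hazard ratio then falls with no difference in disease course, and the false-positive rate of the test that gates ORR and OS rises. A PFS analysis that keeps scan-date progression would carry the same distortion, so agreement among such analyses would not be reassurance.

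**Working it through.** **1. Reproduce the design (Protocol 10.2).** The plan says "a minimum of 264 PFS events are needed to provide 90% power at a 2-sided alpha of 0.05 for the study", with HR 0.67, and assumes that "the median PFS for regorafenib is approximately 5 months".

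- Events (Schoenfeld): D = 4(z₀.₉₇₅ + z₀.₉₀)² / (ln HR)² = 4(1.960 + 1.282)² / (ln 0.67)² ≈ 42.03 / 0.1604 ≈ 262.1, so 263 against 264 stated. Freedman's formula gives 270.
- Power at 264 events: (√264 / 2) × 0.4005 − 1.960 = 8.124 × 0.4005 − 1.960 ≈ 1.294, i.e. 90.2%.
- Patients: reading the scaled accrual parameter as −9/18 = −0.5 per month, with 18 + 6 months, the event probability is 0.588. Then 264 / 0.588 = 449, and 449 / 0.98 = 458 against 460 stated.
- Least extreme significant HR at 264 events: exp(−1.960 × 2 / √264) ≈ 0.79.

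**2. Does any planned PFS analysis change the dating?** (Protocol 10.5.3.1; SAP 4.6.2 and Table 2)

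| Analysis | What it changes | Date of off-schedule progression |
|---|---|---|
| Primary (FDA rules) | - | scan date |
| EMA rules | censoring for new therapy and missed visits | scan date |
| Per-protocol | population | unchanged |
| Unstratified | stratification | unchanged |
| Investigator | reader | unchanged |
| Choi | response criteria | unchanged |

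No interval-censored or scheduled-date analysis, and no by-arm summary of unscheduled scans, appears in the visible text.

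**3. Simulation.** From the plan: 460 patients 1:1, control median 5 months, accrual as above, scans every 56 days ±7 days, cutoff at 264 events. Assumed: exponential PFS, no true effect, and the share of progressions found off schedule (no rate is in the documents). The test is an unstratified log-rank at one-sided 0.025. Avapritinib is fixed at 10% off schedule; 3,000 trials per scenario.

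| Regorafenib share | Scan uniform between PD and next visit: HR, error | Scan at PD: HR, error |
|---|---|---|
| 20% | 0.987, 3.0% | 0.978, 3.3% |
| 30% | 0.969, 4.3% | 0.957, 4.9% |
| 40% | 0.953, 6.0% | 0.936, 6.9% |

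At a true 4%, the Monte Carlo standard error is √(0.04 × 0.96 / 3,000) ≈ 0.4 percentage points. Repeat runs gave errors of 3.4-4.1%, 4.2-6.0% and 6.2-7.7%. Rounded ranges are therefore HR 0.98-0.99, 0.96-0.97 and 0.94-0.95, with error about 3-4%, 4-6% and 6-8%. If 10% of events are deaths (also assumed), the uniform case weakens to 0.989, 0.973 and 0.961, with 2.6%, 3.9% and 4.8%.

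**4. Cross-check by hand.** Error ≈ Φ(−1.960 + 8.124 × |ln HR|).

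- HR 0.985: Φ(−1.960 + 0.123) ≈ 3.3%
- HR 0.965: Φ(−1.960 + 0.289) ≈ 4.7%
- HR 0.945: Φ(−1.960 + 0.460) ≈ 6.7%

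Each falls in the simulated range.

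**5. Direction** (uniform placement, 6,000 trials). 30% in both arms: HR 1.003, error 2.0%. Regorafenib 30%, avapritinib 15%: 0.977, 4.4%. Regorafenib 15%, avapritinib 30%: 1.024, 1.5%.

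**6. Does re-dating remove it?** Every progression was dated to its scheduled assessment and counted only if that date was on or before the cutoff. With 20%, 30% or 50% off schedule on regorafenib and 0% on avapritinib, HR moved from 0.972, 0.960 and 0.930 to 1.001, 1.003 and 1.000, with error 2.2-2.6%. With a true HR of 0.67, 0.658, 0.648 and 0.634 returned to 0.672, 0.670 and 0.672. Re-dating only the off-window progressions, as proposed under the fix, gave HR 0.99-1.00 and error 1.9-3.0%. Moving the date but still counting events re-dated past the cutoff left HR 0.978 and error 4.1% at 50% versus 0%.

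**The case against.** The imbalance is assumed. The scan calendar is the same in both arms and independent of dosing, and an early scan counts only if a blinded reader calls progression. For a new nodule within an existing mass, Appendix 6 asks for at least 2 cm or expansion on two sequential studies, so early scanning will not always give early progression.

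Nor is the incentive one-sided. Section 7.5.1 ties stopping for locally assessed progression to central confirmation in both arms. Avapritinib patients have not had regorafenib (5.3), which section 1.3 calls the only approved TKI after two prior TKIs. Sites may want early confirmation there too.

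All of this stands, and it makes the claim conditional. It does not supply a check: a common calendar does not stop extra scans, and blinded confirmation does not change their date.

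Two stronger readings are tempting. A reader might infer a larger effect from a simulation with scans on an exact 56-day grid and off-schedule scans at the moment of progression: 10% versus 20%, 30% or 40% then gives HR 0.96, 0.93 or 0.91 and error 4.6%, 7.5% or 11.3%. The protocol's ±1 week window rules out that grid, on which every scheduled progression ties and off-schedule ones rank ahead. A reader might also infer that nothing anywhere in the plan addresses this. The SAP's exploratory efficacy section is redacted, and the imaging and IDMC charters are not among the documents, so the statement is limited to the visible text.

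**Conclusion.** The point holds as a conditional risk. The documents establish open-label treatment, a crossover incentive specific to regorafenib, unscheduled scans that feed the primary endpoint, scan-date progression under both censoring sets, and no visible PFS analysis that would reveal an imbalance. They do not establish that an imbalance exists or which way it would run.

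Under the assumed gaps of 10 to 30 percentage points, HR falls by about 0.01 to 0.06 with no true effect, and one-sided error rises to between about 3% and 8%. Each progression moves by less than one scan interval, so the effect is bounded. It is too small by itself to reach the significance threshold of about 0.79, let alone the design HR of 0.67. It matters most if the observed result lies near that threshold. A cheap pre-specified check is warranted; a change to the primary analysis, event target or sample size is not.

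**What to change.** Add to SAP 4.6.2 a pre-specified sensitivity analysis of centrally read mRECIST PFS:

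- Progression seen on a scan outside the ±1 week window of the 8-weekly schedule is dated to the next scheduled scan date. If that date is after the cutoff, the patient is censored at the last scheduled scan.
- The schedule counts from C1D1, or from randomization for ITT patients never dosed.
- Deaths keep their own date.
- The new-therapy and missed-assessment rows of Table 2 are applied with the actual, not the re-dated, progression date. Crossover can begin 7 to 28 days after the last regorafenib dose (Protocol 7.6), so it may precede a re-dated progression. Without this line, the FDA new-therapy row could censor re-dated events, mainly in the regorafenib arm.
- The stratified log-rank test and Cox model are unchanged.

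Tabulate by arm the number and timing of unscheduled scans and of progressions first seen on them. If the arms are alike, the table supports the primary result. The primary dating rule stays.

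Cost: one SAP paragraph, one table and one extra run on data already collected. Progression dates are coarser and medians slightly longer, in this sensitivity analysis only.
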